5.2.1 Reporting of Pregnancy and Lactation to the Sponsor

Although pregnancy and lactation are not considered adverse events, it is the responsibility of investigators or their designees to report any pregnancy or lactation in a subject (spontaneously reported to them) that occurs during the trial.

Pregnancies and lactations that occur after the consent form is signed but before treatment allocation/randomization must be reported by the investigator if they cause the subject to be excluded from the trial, or are the result of a protocol-specified intervention, including but not limited to washout or discontinuation of usual therapy, diet, placebo treatment or a procedure.

Pregnancies and lactations that occur from the time of treatment allocation/randomization through 120 days following cessation of Sponsor's product, or 100 days following cessation of treatment if the subject initiates new anticancer therapy, including during at least 5 half-lives after product administration, whichever is earlier, must be reported by the investigator. All reported pregnancies must be followed to the completion/termination of the pregnancy. Pregnancy outcomes of spontaneous abortion, missed abortion, benign hydatidiform mole, blighted ovum, fetal death, intrauterine death, miscarriage and stillbirth must be reported as

serious events (Important Medical Events). If the pregnancy continues to term, the outcome (health of infant) must also be reported.

Such events must be reported within 24 hours to the Sponsor and within 24 hours (1 business day) to BMS and Pfizer Global Safety.

5.2.2 Immediate Reporting of Adverse Events to the Sponsor and to BMS and Pfizer

If any SAE meets FDA/IRB reporting guidelines, we would transfer the information onto a Medwatch form for submission to BMS and/or Pfizer.

5.2.2.1 Serious Adverse Events

A serious adverse event is any adverse event occurring at any dose or during any use of nivolumab and/or axitinib that:

- Results in death;
- Is life threatening;
- Results in persistent or significant disability/incapacity;
- Results in or prolongs an existing inpatient hospitalization;
- Is a congenital anomaly/birth defect;
- Suspected transmission of an infectious agent (e.g., pathogenic or nonpathogenic) via the study drug;
- Is another important medical event
- Note: In addition to the above criteria, adverse events meeting either of the below criteria, although not serious per ICH definition, are reportable to Sponsor in the same timeframe as SAEs to meet certain local requirements. Therefore, these events are considered serious by the Sponsor for collection purposes.
 - Is a new cancer (that is not a condition of the study);
 - Is associated with an overdose.

THE FOLLOWING HOSPILIZATIONS ARE NOT CONSIDERED SAEs:

- a visit to the emergency room or other hospital department < 24 hours, that does not result in admission (unless considered an important medical or life-threatening event)
- elective surgery, planned prior to signing consent
- admissions as per protocol for a planned medical/surgical procedure
- routine health assessment requiring admission for baseline/trending of health status (eg, routine colonoscopy)
- Medical/surgical admission other than to remedy ill health and planned prior to entry into the study. Appropriate documentation is required in these cases.

- Admission encountered for another life circumstance that carries no bearing on health status and requires no medical/surgical intervention (eg, lack of housing, economic inadequacy, caregiver respite, family circumstances, administrative reason).
- Admission for administration of anticancer therapy in the absence of any other SAEs (applies to oncology protocols)

The Sponsor will reconcile the clinical database SAE cases (case level only) transmitted to BMS Global Pharmacovigilance ([contact]). Frequency of reconciliation should be every 3 months and prior to the database lock or final data summary. BMS GPV&E will email, upon request from the Investigator, the GPV&E reconciliation report. Requests for reconciliation should be sent to [contact]. The data elements listed on the GPV&E reconciliation report will be used for case identification purposes. If the Investigator determines a case was not transmitted to BMS GPV&E, the case should be sent immediately to BMS.

Refer to Table 3 in Section 4.2.4 for additional details regarding each of the above criteria.

For the time period following the subject's written consent to participate in the study through 100 days of discontinuation of dosing, any serious adverse event, or follow up to a serious adverse event, including death due to any cause other than progression of the cancer under study (reference Section 7.2.3.3 for additional details) that occurs to any subject must be reported within 24 hours to the Sponsor and within 24 hours or 1 business day to BMS and Pfizer Global Safety if it causes the subject to be excluded from the trial, or is the result of a protocol-specified intervention, including but not limited to washout or discontinuation of usual therapy, treatment or a procedure.

For the time period beginning at treatment allocation/randomization through 100 days following cessation of treatment with nivolumab, or until the participant initiates new anticancer therapy, whichever is earlier, any serious adverse event, or follow up to a serious adverse event, including death due to any cause other than progression of the cancer under study (reference Section 7.2.3.3 for additional details), whether or not related to study treatment, must be reported within 24 hours to the Sponsor and within 24 hours or 1 business day to BMS and Pfizer Global Safety.

Additionally, any serious adverse event, considered by an investigator who is a qualified physician to be related to treatment that is brought to the attention of the investigator at any time following consent through the end of the specified safety follow-up period specified in the paragraph above, or at any time outside of the time period specified in the previous paragraph also must be reported immediately to the Sponsor and to BMS and Pfizer Global Safety.

REPORTING OF SERIOUS ADVERSE EVENTS

5.2.2.2 Events of Clinical Interest

Selected non-serious and serious adverse events are also known as Events of Clinical Interest (ECI) and must be reported within 24 hours to the Sponsor and within 2 working days to BMS Global Safety.

For the time period beginning when the consent form is signed until treatment allocation/randomization, any ECI, or follow up to an ECI, that occurs to any subject must be

reported within 24 hours to the Sponsor and within 24 hours/1 business day to BMS and Pfizer Global Safety if it causes the subject to be excluded from the trial, or is the result of a protocol-specified intervention, including but not limited to washout or discontinuation of usual therapy, diet, placebo treatment or a procedure.

For the time period beginning at treatment allocation/randomization through 100 days following cessation of treatment, or 30 days following cessation of treatment if the subject initiates new anticancer therapy, whichever is earlier, any ECI, or follow up to an ECI, whether or not related to treatment, must be reported within 24 hours to the Sponsor and within 24 hours to BMS and Pfizer Global Safety.

Events of clinical interest for this trial include:

- 1. An overdose of nivolumab or axitinib, as defined in Section 7.2.1 Definition of an Overdose for This Protocol and Reporting of Overdose to the Sponsor, that is not associated with clinical symptoms or abnormal laboratory results.
- 2. An elevated AST or ALT lab value that is greater than or equal to 3X the upper limit of normal and an elevated total bilirubin lab value that is greater than or equal to 2X the upper limit of normal and, at the same time, an alkaline phosphatase lab value that is less than 2X the upper limit of normal, as determined by way of protocol-specified laboratory testing or unscheduled laboratory testing.*

*Note: These criteria are based upon available regulatory guidance documents. The purpose of the criteria is to specify a threshold of abnormal hepatic tests that may require an additional evaluation for an underlying etiology.

5.2.2.3 Protocol-Specific Exceptions to Serious Adverse Event Reporting

Efficacy endpoints as outlined in this section will not be reported to BMS and Pfizer as described in Section 7.2.3.- Immediate Reporting of Adverse Events to the Sponsor and to BMS and Pfizer, unless there is evidence suggesting a causal relationship between the drug and the event. Any such event will be submitted to the Sponsor within 24 hours and to BMS and Pfizer Global Safety within 2 working days either by electronic or paper media.

Specifically, the suspected/actual events covered in this exception include any event that is disease progression of the cancer under study.

The Sponsor will monitor unblinded aggregated efficacy endpoint events and safety data to ensure the safety of the subjects in the trial. Any suspected endpoint which upon review is not progression of the cancer under study will be forwarded to BMS and Pfizer Global Safety as a SAE within 2 working days of determination that the event is not progression of the cancer under study.

Hospitalization related to convenience (e.g., transportation issues etc.) will not be considered a SAE.

5.2.3 Evaluating Adverse Events

An investigator who is a qualified physician will evaluate all adverse events according to the NCI Common Terminology for Adverse Events (CTCAE), version 5.0. Any adverse event which changes CTCAE grade over the course of a given episode will have each change of grade recorded on the adverse event case report forms/worksheets.

All adverse events regardless of CTCAE grade must also be evaluated for seriousness.

Table 8: Evaluating Adverse Events

An investigator who is a qualified physician, will evaluate all adverse events as to:

V4.0 CTCAE Grading	Grade 1	Mild; asymptomatic or mid symptoms; clinical or diagnostic observations only; intervention not indicated.	
	Grade 2	Moderate; minimal, local or noninvasive intervention indicated; limiting age-appropriate instrumental ADL.	
	Grade 3	Severe or medically significant but not immediately life-threatening; hospitalization or prolongation or hospitalization indicated; disabling; limiting self-care ADL.	
	Grade 4	Life threatening consequences; urgent intervention indicated.	
	Grade 5	Death related to AE	
Seriousness	A serious adverse event is any adverse event occurring at any dose or during the course of study treat that:		
	†Results in dea	ath; or	
	†Is life threatening; or places the subject, in the view of the investigator, at immediate risk of death from the event as it occurred (Note: This does not include an adverse event that, had it occurred in a more severe form, might have caused death.); or		
		persistent or significant disability/incapacity (substantial disruption of one's ability to life functions); or	
	†Results in or prolongs an existing inpatient hospitalization (hospitalization is defined as an inpatient admission, regardless of length of stay, even if the hospitalization is a precautionary measure for continued observation. (Note: Hospitalization for an elective procedure to treat a pre-existing condition that has not worsened is not a serious adverse event. A pre-existing condition is a clinical condition that is diagnosed prior to the use of study treatment and is documented in the patient's medical history.); or		
	†Is a congenit diagnosis);or	al anomaly/birth defect (in offspring of subject taking the product regardless of time to	
	Is a new cancer	r (that is not a condition of the study) (although not serious per ICH definition, is reportable);	
	Is an overdose (whether accidental or intentional). Any adverse event associated with an overdose is considered a serious adverse event for collection purposes. An overdose that is not associated with an adverse event is considered a non-serious event of clinical interest and must be reported within 24 hours to the Sponsor and to BMS and Pfizer within 2 working days.		
	hospitalization the event may j	ant medical events that may not result in death, not be life threatening, or not require may be considered a serious adverse event when, based upon appropriate medical judgment, eopardize the subject and may require medical or surgical intervention to prevent one of the previously (designated above by a †).	
Duration	Record the start and stop dates of the adverse event. If less than 1 day, indicate the appropriate length of time and units		

5.2.4 Sponsor Responsibility for Reporting Adverse Events

All Adverse Events will be reported to regulatory authorities, IRB/IECs and investigators in accordance with all applicable global laws and regulations.

6.0 STATISTICAL CONSIDERATION

6.1 Study Design

This is a single arm phase II clinical trial to test the efficacy of nivolumab plus axitinib in patients with advanced melanoma who have progressed on anti-PD1 (+/- anti-CTLA4). The primary endpoint of this study is the object response rate (ORR). We use Simon's minimax two-stage design as detailed in Section 6.3.

6.2 Safety monitoring

The combination of pembrolizumab plus axitinib has been approved by FDA for advanced renal cell carcinoma, and its toxicity profile has been well established. In this study, we will use nivolumab in place of pembrolizumab, and we expect these two drugs are very similar, thus we expect the toxicity rate of the current combination therapy and dose is acceptable, so we don't think it necessary to conduct a phase I dose-finding study. However, to be cautious, we will 1) use a Bayesian monitoring scheme and 2) incorporate a trial stopping rule into the protocol. The Bayesian monitoring scheme will continuously monitor the rate of severe adverse events (SAE). The SAE is defined as grade 3 and higher toxicity that are attributable to the combination therapy. A non-informative prior of Beta(1, 1) for the SAE rate will be used. We will hold the recruit if the posterior probability Pr(SAE rate>30%)>=0.7 and the study committee and the PI will decide whether to modify or discontinue the study. The stopping boundary for toxicity is given in the following table:

Number of SAEs >=	in Number of Patients =
2	3-5
3	6-8
4	9-11
5	12-14
6	15-17
7	18-20
8	21-23
9	24-26

10	27-29
11	30-31

We simulate the operating characteristics under various assumed true toxicity rate (see the following table):

Scenario	True Prob.	Prob. of	Average	Average
	of SAE	Early	Num. of Patients	Num. of SAE
		Stopping	Patients	SAE
1	0.1	0.10	28	3
2	0.2	0.37	22	4
3	0.3	0.71	14	4
4	0.4	0.93	8	3

Regarding the analysis of safety, we will consider a toxicity event to be an adverse event (evaluated by CTCAE 5.0) that is possibly, probably, or definitely related to treatment. The maximum grade of toxicity for each category of interest will be recorded for each patient and the summary results will be tabulated by category and grade.

If one Grade 5 event or two Grade 4 events for AEs considered at least possibly related to combination study therapy (possibly attributed to each drug) occur, the trial will be halted to accrual and a thorough safety analysis will be conducted prior to enrolling new patients.

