6.3 Sample Size and Accrual

The null hypothesis that the true ORR is 10% will be tested versus a one-sided alternative of 25% or higher, using Simon's minimax two-stage design. In the first stage, 16 patients will be accrued. If there are <2 responses, the study will be stopped and alternative doses of axitinib considered. If at least 2 responses are observed, 15 additional patients will be enrolled in the 2nd stage. The combination therapy will be regarded as worthy of further study if ≥6 responses are observed in both stages. Total sample size is 31 patients. This design has a type I error rate of 0.08 with a power of 0.81 when the true response rate is 0.25. Secondary endpoints of this study are PFS, OS and safety. Survival endpoints (PFS and OS) will be estimated with the Kaplan-Meier method, and compared between marker value groups with the log-rank test. We will also perform extensive correlative analysis (flow, IHC, metabolic analyses).

The accrual rate of the trial is estimated to be 1-2 patients/month, therefore, we will be able to finish the accrual of the study in approximately 24 months.

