8.0 ADMINISTRATIVE AND REGULATORY DETAILS

8.1 DATA SAFETY AND MONITORING PLAN

Investigator/Sub-investigators, regulatory, CRS management, clinical research coordinators, clinical research associates, data managers, and clinic staff meet monthly in disease center

Data Safety Monitoring Boards (DSMB) to review and discuss study data to include, but not limited to, the following:

- Serious adverse events
- Subject safety issues
- Recruitment issues
- Accrual
- Protocol deviations
- Unanticipated problems
- Breaches of confidentiality

Minutes from the disease center DSMB meetings are available to those who are unable to attend in person.

All toxicities encountered during the study will be evaluated on an ongoing basis according to the NCI Common Toxicity Criteria version 5.0. All study treatment associated adverse events that are serious, at least possibly related and unexpected will be reported to the IRB. A set of Bayesian continuous monitoring stopping rules will be implemented to ensure that the true severe adverse event (SAE) rate is controlled under 30% (see section 7). Any modifications necessary to ensure subject safety and decisions to continue, or close the trial to accrual are also discussed during these meetings. If any literature becomes available which changes the risk/benefit ratio or suggests that conducting the trial is no longer ethical, the IRB will be notified in the form of an Unanticipated Problem submission and the study may be terminated.

All study data reviewed and discussed during these meetings will be kept confidential. Any breach in subject confidentiality will be reported to the IRB in the form of an Unanticipated Problem submission. The summaries of these meetings are forwarded to the UPCI DSMC which also meets monthly following a designated format.

For all research protocols, there will be a commitment to comply with the IRB's policies for reporting unanticipated problems involving risk to subjects or others (including adverse events). DSMC progress reports, to include a summary of all serious adverse events and modifications, and approval will be submitted to the IRB at the time of renewal.

Protocols with subjects in long-term (survival) follow-up or protocols in data analysis only, will be reviewed twice a year rather than monthly.

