Both the UPCI DSMC as well as the individual disease center DSMB have the authority to suspend accrual or further investigate treatment on any trial based on information discussed at these meetings.

All records related to this research study will be stored in a locked environment. Only the researchers affiliated with the research study and their staff will have access to the research records

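### Does the Bayesian toxicity hold rule in Section 6.2 need a stated starting patient, given that its wording is met by one SAE in patient 1 or 2 while its boundary table begins at patient 3?

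*Combined protocol and SAP*

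**What the plan says.** Section 6.2 (Safety monitoring) sets up continuous monitoring of the rate of SAEs, defined there as toxicity of grade 3 or higher attributable to the combination. The prior is given: "A non-informative prior of Beta(1, 1) for the SAE rate will be used". The criterion is "We will hold the recruit if the posterior probability Pr(SAE rate>30%)>=0.7", after which "the study committee and the PI will decide whether to modify or discontinue the study". The section then says "The stopping boundary for toxicity is given in the following table". The first row of that table is 2 or more SAEs in 3-5 patients and the last is 11 or more in 30-31. There is no row for 1 or 2 patients. A second table gives operating characteristics at true SAE rates 0.1, 0.2, 0.3 and 0.4.

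The same section has a separate halt to accrual for one Grade 5 event or two Grade 4 events at least possibly related to the combination. It carries no minimum number of patients.

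Section 8.1 repeats that "A set of Bayesian continuous monitoring stopping rules will be implemented" and adds that "Both the UPCI DSMC as well as the individual disease center DSMB have the authority to suspend accrual"; both bodies meet monthly. Section 6.3 gives the pace: "The accrual rate of the trial is estimated to be 1-2 patients/month". No section states the patient from which the Bayesian rule applies.

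**The concern.** The words and the table appear to give different instructions for the first two patients. Under the words, a single SAE in patient 1 or 2 puts the posterior probability above 0.70 and calls for a hold. The table has no entry there, and the printed operating characteristics assume no hold for one SAE at that point. The plan relies on this scheme as one of two safeguards in place of a phase I dose-finding study, so staff should be able to tell whether the first SAE triggers it. If the words governed and every hold were final, the printed stopping probabilities would be too low, most visibly at low true rates: 0.22 against the printed 0.10 at a true rate of 0.1.

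**Working it through.** **Inputs.** From Section 6.2: Beta(1,1) prior, threshold rate 0.30, cut-off 0.70, the boundary table and the operating characteristics. From Section 6.3: maximum 31 patients, 1-2 patients per month.

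**Posterior.** With x SAEs in n patients the SAE rate has posterior Beta(1+x, 1+n-x). The rule looks at the probability that this exceeds 0.30.

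- 0 patients: Beta(1,1), 1 - 0.30 = 0.70 exactly
- 1 SAE in 1: Beta(2,1), 1 - 0.30² = 0.910
- 1 in 2: Beta(2,2), 1 - (3×0.30² - 2×0.30³) = 1 - 0.216 = 0.784
- 1 in 3: Beta(2,3), 0.70⁴ + 4×0.30×0.70³ = 0.2401 + 0.4116 = 0.652
- 2 in 3: Beta(3,2), 0.6517 + 6×0.30²×0.70² = 0.6517 + 0.2646 = 0.916

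**Boundary.** The smallest x giving at least 0.70 was found for each n. From n = 3 to n = 31 it equals the printed boundary every time. It differs only at n = 1 and n = 2, where it is x = 1 and the table has no entry.

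**Operating characteristics.** These come from an exact recursion, one patient at a time up to 31, with every crossing treated as a final stop.

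| True SAE rate | 0.1 | 0.2 | 0.3 | 0.4 |
|---|---|---|---|---|
| Printed: stopping | 0.10 | 0.37 | 0.71 | 0.93 |
| Table from patient 3: stopping | 0.096 | 0.366 | 0.709 | 0.928 |
| Printed: mean patients | 28 | 22 | 14 | 8 |
| Table from patient 3: mean patients | 28.48 | 21.92 | 14.04 | 8.18 |
| Printed: mean SAEs | 3 | 4 | 4 | 3 |
| Table from patient 3: mean SAEs | 2.85 | 4.38 | 4.21 | 3.27 |
| Words from patient 1: stopping | 0.222 | 0.495 | 0.776 | 0.946 |
| Words from patient 1: mean patients | 24.59 | 17.31 | 10.38 | 5.58 |

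The printed figures are reproduced by the table and not by the words applied from patient 1. The gap in stopping probability is 0.126, 0.130, 0.068 and 0.018.

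**How often the two readings could part.** With p the true SAE rate, the chance that patient 1 or 2 ever has an SAE is 1 - (1-p)² = 0.19, 0.36, 0.51, 0.64. It splits in two:

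- The table also holds at patient 3 (at least 2 SAEs in 3): 3p²(1-p) + p³ = 0.028, 0.104, 0.216, 0.352.
- Exactly one SAE in the first two and none in the third: 2p(1-p)² = 0.162, 0.256, 0.294, 0.288. Here the words are no longer met at patient 3, since 1 in 3 gives 0.652.

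**Why these are ceilings.** They count an SAE at any time in patients 1 and 2. The words are met only if the event is known while the count is still 1 or 2. Patient 3 enters about 1 month (at 2 per month) to 2 months (at 1 per month) after patient 1, while treatment lasts up to 2 years (Section 4.2.3) and adverse events are reported to 100 days after it ends, or until new anticancer therapy if earlier (Section 5.2). A single SAE in patient 1 or 2 that comes to light once patient 3 is counted is judged as 1 in 3, which does not meet the rule. The number of extra holds could therefore be close to zero.

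**The case for a change.** The best argument for a change is that the criterion is a complete sentence, the monitoring is described as continuous, and the table is silent for patients 1 and 2; it does not say that no hold applies. A careful reader could hold after the first SAE and be following the text. The monthly committees have discretion to suspend accrual but do not supply the missing number. The Grade 4/5 halt does not close the gap either, because a Grade 3 event or a single Grade 4 event in patient 1 or 2 counts as an SAE without triggering that halt. One sentence would settle it.

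All of that is factually right: the start is not stated. One further point stands. The operating characteristics alone do not fix the start at 3, because also holding at 2 SAEs in 2 patients gives the same stopping probabilities and mean numbers of 28.47, 21.88, 13.95 and 8.02, which round to the same print. The start is shown by the table's first row.

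What does not stand is that the sentence is a competing instruction. Run without the table, it is met at exactly 0.70 before the first patient is treated, so recruitment could never open. It explains how the boundary was derived; the table that follows is the boundary to be applied.

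**Conclusion.** No change is needed. This is a small gap that the section itself fills. The named boundary starts at 3 patients, agrees with the worded criterion at all 29 sample sizes from 3 to 31, and yields the printed properties. A team that follows it gets exactly the monitoring the plan describes.

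The discrepancy is confined to patients 1 and 2. At true rates 0.1, 0.2, 0.3 and 0.4 the chance of an extra or earlier hold is at most 0.19, 0.36, 0.51 and 0.64, reached only if every SAE in those patients is known before patient 3 is counted. Stopping of 0.22, 0.50, 0.78 and 0.95 further assumes that no hold is ever lifted, although the plan sends each hold to the study committee and the PI for a decision. If such holds are reviewed and lifted, the printed figures stand. The Grade 5 / two Grade 4 halt applies from the first patient, so what lies outside both rules is a Grade 3 event or a single Grade 4 event, with monthly review still in place.

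Stating the start would record what the table's first row shows and alter no figure. Adding entries for 1 and 2 patients would create a different rule, one that reacts to a single early SAE, and reasonable statisticians would disagree on it. Neither affects the primary endpoint, the sample size or the boundary from patient 3 on. This conclusion assumes that the table is the operative boundary, as Section 6.2 says.
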